12.7 Safety Variables and Analyses

12.7.1.1 Adverse Events

AEs will be summarised for all GBCAs pooled, for non-Clariscan GBCAs pooled, and for all individual GBCAs administered during the study, including Clariscan. AEs and SAEs will be coded using Medical Dictionary for Regulatory Activities (MedDRA) and all reported events will be listed for the Safety Analysis Set. Immediate treatment-emergent AEs (TEAE) are defined as AEs that occur from the time of treatment administration through 1 hour after administration. Delayed TEAEs are defined as AEs that occur later than 1 hour post-administration up to 7 days post-administration.

The number and percentage of patients with 1 or more AEs will be summarised by system organ class and preferred term. Summaries will also be presented by AE intensity and judged relationship to study drug. Treatment-emergent SAEs will be presented by treatment group for the safety population.

12.8 Interim Analysis

No interim analyses are planned for this study.

12.9 Sample Size Calculation

This is an observational study to understand the pattern of use of GBCAs use in CE-MR. The sample size is not based on statistical considerations, as the study does not formally test a hypothesis. Recruitment will be open for 3 months (90 days), with a cap on the maximum number of patients recruited by each centre (Table 1), and all consecutive patients who provide informed consent from the start of study (after Clariscan is on formulary in the study centre and available for routine clinical use) will be enrolled. Even if the centre has not enrolled the maximum number of patients allocated for that centre, recruitment will close at the end of the 90-day enrolment period regardless of the number of patients enrolled. It is anticipated that up to 5,400 patients from European countries where Clariscan has been launched will be enrolled. The maximum number of patients per country can be found in Table 1.

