
Number of Subjects/Centres Planned: Up to 5,400 patients in 14 centres in Europe: Germany (2 centres, 300-600 patients per centre), Poland (3 centres, 300 patients), Spain (3 centres, 200-500 patients), Italy (3
		

Name of Sponsor/Company: GE Healthcare Ltd. and its Affiliates	Individual Study Table Referring to Part of Dossier in Which the Individual Study or Study Table is Presented: Volume: Reference:	(For National Authority Use Only)
Name of Finished Product: Clariscan 0.5 mmol/ml Solution for Injection		
Name of Active Ingredient: Gadoteric acid (as gadoterate meglumine): 1, 4, 7, 10 tetraazacyclododecane N, N', N'', N''' tetraacetic acid gadolinium complex		
centres, 100-500 patients), France (1 centre, 250 patients), Norway (1 centre, 200 patients), Portugal (1 centre, 300 patients).		
CE-MR Imaging of Subjects: 
 • Medicinal Product: Clariscan as per SPC; other GBCAs as prescribed • Duration of Treatment: at the time of injection of GBCA and immediately after that with spontaneous reporting of AEs up to 7 days; no active follow-up 		

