
Name of Sponsor/Company: GE Healthcare Ltd. and its Affiliates	Individual Study Table Referring to Part of Dossier in Which the Individual Study or Study Table is Presented: Volume: Reference:	(For National Authority Use Only)
Name of Finished Product: Clariscan 0.5 mmol/ml Solution for Injection		
Name of Active Ingredient: Gadoteric acid (as gadoterate meglumine): 1, 4, 7, 10 tetraazacyclododecane N, N', N'', N''' tetraacetic acid gadolinium complex		

AEs will be summarised for all GBCAs pooled, for non-Clariscan GBCAs pooled, and for all individual GBCAs administered during the study, including Clariscan. AEs and SAEs will be coded using Medical Dictionary for Regulatory Activities (MedDRA) and all reported events will be listed for the Safety Analysis Set. Immediate treatment-emergent AEs (TEAE) are defined as AEs that occur from the time of treatment administration through 1 hour after administration. Delayed TEAEs are defined as AEs that occur later than 1 hour post-administration up to 7 days post-administration.

The number and percentage of patients with 1 or more AEs will be summarised by system organ class and preferred term. Summaries will also be presented by AE intensity and judged relationship to study drug. Treatment-emergent SAEs will be presented by treatment group for the safety population.

Sample Size:

This is an observational study to understand the pattern of use of GBCAs use in CE-MR. The sample size is not based on statistical considerations, as the study does not formally test a hypothesis. Recruitment will be open for 3 months (90 days), with a cap on the maximum number of patients recruited by each centre (Table 1), and all consecutive patients who provide informed consent from the start of study (after Clariscan is on formulary in the study centre and available for routine clinical use) will be enrolled. Even if the centre has not enrolled the maximum number of patients allocated for that centre, recruitment will close at the end of the 90-day enrolment period regardless of the number of patients enrolled. It is anticipated that up to 5,400 patients from European countries where Clariscan has been launched will be enrolled. The maximum number of patients per country can be found in Table 1.

Table 1 Maximum Number of Patients Per Country

Country	Number of Centres	Maximum Number of Patients Allocated to Centres
Norway	1	200
Germany	2	300 + 600 = 900
Spain	3	500 x 2 + 200 = 1200
Italy	3	500 + 400 + 100 = 1000
Portugal	1	300

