6 STUDY DESIGN

6.1 Overall Study Design and Plan

A cross-sectional, multicentre (17 European Union [EU] centres), observational study with prospective data collection in patients undergoing contrast-enhanced MR (CE-MR) examination as part of routine clinical practice. Patients will be invited to participate in the study only after the decision has been made by the physician to use contrast agents and Clariscan is already included in the formulary of the hospital/institution as an independent decision prior to investigator taking part in this study. Patients enrolled in the study will not be actively followed up to collect adverse events (AEs) or outcomes. Any spontaneously reported AEs/information will be recorded/reported by the investigators up to 7 days after the MR procedure.

Enrolment

Patients: patients will only be approached to participate in the study after the physician has decided to use GBCA as part of routine clinical practice. Only patients who provide consent (directly or via a person with legal responsibility) will then be included in the study. To enable an understanding of the benefit of GBCAs use in a real world clinical setting the study plan to capture information in a maximum of 5,400 consecutive patients after the study centre has accepted to use Clariscan as an independent decision.

Recruitment will be based on **time (maximum 3 months – a month is equal to 30 calendar days) with a cap of a maximum number of cases per centre by country as defined in Table 1**. It will include all consecutive patients from the start of study after the Clariscan is on formulary of the study centre and available for routine clinical use. The decision to use GBCAs in the study centre/investigator will be made independent of the study after the centre has included Clariscan in the hospital/institution formulary.

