7 SELECTION AND WITHDRAWAL OF SUBJECTS

7.1 Procedures for Enrolment

After the start of the study all consecutive consenting adult and paediatric, male and female patients, undergoing MR procedures whose physician has made the decision to use GBCA as part of routine clinical practice will be enrolled. The enrolment of the total number of patients per centre will be limited to a defined number of patients for a centre (Table 1) with a maximum duration of recruitment of 3 months (month = 30days) from start date, i.e., first patient recruitment.

A subgroup of initial patients will be selected to transfer the anonymised images to GE Healthcare (GEHC) through AGMednet. The images will be archived at GEHC and analysed at a later date by an expert MR radiologist panel to assess the quality of images. The first 50 images will be transferred in a 1:1 ratio for Clariscan and other GBCAs, i.e., first consecutive 25 images (25 maximum or total recruited in 3 months) for Clariscan and other GBCAs. If sufficient number of images (25) for either group (Clariscan or other GBCAs) are not acquired in 3 months, the recruitment will stop at 3 months and all images will be transferred for the blinded read, the comparative analysis is not at centre level. All images will be pooled together for blinded image read by the expert panel.

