A subgroup of patients will be selected to transfer the anonymised images to GEHC through AGMednet. The images will be archived at GEHC to be analysed at a later date by an expert MR radiologist panel to assess the quality of images. The first 50 images will be transferred in 1:1 ratio for Clariscan and other GBCAs, i.e., the first consecutive 25 images for Clariscan and the first consecutive 25 images of the other GBCAs (excluding liver-specific GBCAs). In total, a maximum of 850 patients' images will be transferred from all study centres. If sufficient number of images (25) for Clariscan or other GBCA group are not acquired in 3 months, the recruitment will stop at 3 months and all images for either group will be transferred for blinded read.

- Collective anonymised and blinded images for all GBCAs including Clariscan from all centres will be assessed and analysed by a panel of 3 MR expert radiologists. There will be no centre-level analysis or comparison for Clariscan and other GBCAs.
- Quality of images reported by 3 MR expert radiologists blinded to the GBCAs use and inter-observer variability.
- Correlation between local radiologist rating and blinded radiologist rating.

This analysis will not be part of the initial read out of the study and will be performed at a later date.

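### The stated maximum of 5,400 patients cannot be reached under the centre caps in Table 1, which sum to 4,750, and the centre count, image ceiling and Poland entries do not agree with each other

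*Protocol*

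**What the plan says.** **Patients.** Section 12.9 states "It is anticipated that up to 5,400 patients from European countries where Clariscan has been launched will be enrolled", and the sample size paragraph of the synopsis says the same. The synopsis entry on planned numbers reads "Up to 5,400 patients in 14 centres in Europe". Section 6.1 refers to "a maximum of 5,400 consecutive patients".

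**Caps.** Recruitment runs for 90 days, "with a cap on the maximum number of patients recruited by each centre (Table 1" being the second limit in Section 12.9. Section 7.1 says that enrolment per centre "will be limited to a defined number of patients for a centre (Table 1". Table 1 is printed in the synopsis and again in Section 6.1, with an allocation for each country, for example "500 x 2 + 200 = 1200" for Spain.

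**Centres.** The synopsis gives 14, both in its list of centres and in its planned numbers. Section 6.1 opens with "A cross-sectional, multicentre (17 European Union [EU] centres), observational study with prospective data collection".

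**Images.** Section 6.2 plans to archive the first 50 cases from each centre (25 Clariscan and 25 other agents, per Section 6.1). Section 10.2 adds "In total, a maximum of 850 patients' images will be transferred from all study centres", and the synopsis gives the same ceiling.

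**Poland.** Table 1 in the synopsis lists 3 centres and 300 x 3 = 900. Table 1 in Section 6.1 lists 1 centre beside the same product. The synopsis entry on planned numbers gives three centres and a figure of 300 patients, without saying whether that is per centre or in total.

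**The concern.** A maximum that is limited by centre caps should equal the sum of those caps, or be no larger than that sum. Here it is larger. The centre count and the image ceiling should also follow from the same list of centres, and they do not.

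What is at stake is the description of the study, not its inference. Ethics committees and authorities who receive the protocol are told a study size, a number of centres and a volume of image transfer that cannot all be true together. The Stage 2 reading panel would be planned for more images than the listed centres can supply. The caps also decide when a centre stops enrolling, so the conflicting Polish entries leave it open to misreading whether 300 applies to each centre or to the whole country.

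**Working it through.** **Inputs.** Caps come from Table 1 (synopsis and Section 6.1), the patient maximum from Sections 6.1 and 12.9 and the synopsis, images per centre from Section 6.2, and the image ceiling from Section 10.2 and the synopsis.

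| Country | Centres, synopsis table | Centres, Section 6.1 table | Cap (both tables) |
|---|---|---|---|
| Norway | 1 | 1 | 200 |
| Germany | 2 | 2 | 300 + 600 = 900 |
| Spain | 3 | 3 | 500 x 2 + 200 = 1,200 |
| Italy | 3 | 3 | 500 + 400 + 100 = 1,000 |
| Portugal | 1 | 1 | 300 |
| France | 1 | 1 | 250 |
| Poland | 3 | 1 | 300 x 3 = 900 |
| **Sum** | **14** | **12** | **4,750** |

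**1. Attempt to reproduce 5,400.** Sum of caps = 200 + 900 + 1,200 + 1,000 + 300 + 250 + 900 = 4,750. The shortfall is 5,400 - 4,750 = 650, and 650 / 5,400 = 12.0%. The figure is not reproduced.

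**2. Other routes to 5,400.**
- Every centre at the top of its range in the synopsis text: 2 x 600 + 3 x 300 + 3 x 500 + 3 x 500 + 250 + 200 + 300 = 5,850. This is too high, and it overrides the individual caps.
- The same with Poland at 300 in total: 5,850 - 600 = 5,250. This is closer, but it is not 5,400 and it contradicts Table 1.
- Inflation for dropout: 4,750 / (1 - 0.12) = 5,398. This would need a dropout rate of about 12%. The protocol states no rate, the caps apply to patients recruited, and Section 7.4.1 does not replace withdrawals.

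**3. Centre count.** The synopsis table sums to 1 + 2 + 3 + 3 + 1 + 1 + 3 = 14, which matches the synopsis text. The Section 6.1 table sums to 12 because of the Polish row. Neither sum gives the 17 stated in Section 6.1.

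**4. Image ceiling.** 850 / 50 = 17, so the ceiling matches 17 centres. For 14 centres it is 14 x 50 = 700, which is 150 lower, and 150 / 850 = 17.6%.

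**5. Would 17 centres reconcile everything?** Three further centres would have to carry 650 patients, about 217 each. That is within the range of the existing caps (100 to 600), but no such centres are listed.

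**The case against.** The strongest reply is that nothing in the analysis depends on 5,400. Section 12.9 says that the size has no statistical basis and that no hypothesis is formally tested. Recruitment is governed by the 90-day window and the caps, and the country totals agree in both printings of Table 1. The figures of 5,400 and 850 are also worded as ceilings, so enrolling 4,750 patients or transferring 700 images would breach neither. All of this stands, and it limits the weight of the point. It does not make the figures consistent, because a ceiling that full recruitment at every centre cannot reach is misstated.

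Some stronger readings are not supported:

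- *The study's precision is overstated.* The protocol makes no precision statement. As an illustration only, under simple random sampling the 95% half-width for a proportion of 50% is 1.96 x sqrt(0.25 / n). That is 1.33 percentage points at 5,400 and 1.42 at 4,750, a small change.
- *None of the size figures follows from the plan.* The count of 14 agrees with the synopsis table, and 850 follows from 17 centres at 50 each.
- *Poland has one centre, so the study has 12 centres and at most 4,150 patients.* The single centre stands beside 300 x 3, and the synopsis gives three Polish centres throughout. It reads as an error in one cell.
- *The figures 5,400, 17 and 850 are left over from a 17-centre version.* The arithmetic would allow this, but the protocol does not say so or show which count is current.
- *The blinded read is compromised.* Stage 2 is outside the initial read-out, will have its own analysis plan, and already allows fewer images where a group does not reach 25.

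**Conclusion.** The point holds as an internal inconsistency. Under the caps in Table 1 the largest possible enrolment is 4,750, which is 650 or 12.0% below the stated 5,400. For the 14 listed centres the image ceiling is 700, which is 150 or 17.6% below the stated 850. The count of 17 centres in Section 6.1 conflicts with the 14 in the synopsis, and the Polish entries conflict with one another.

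This rests on three assumptions: the caps bind, as Sections 7.1 and 12.9 say; Table 1 lists every centre; and Poland has three centres at 300 each, as its own product shows. No test, power figure or analysis set is affected. It should be corrected, but it does not threaten the study's conclusions.

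**What to change.** Decide which centre count is current, then make the figures agree in the synopsis (list of centres, planned numbers, Stage 2 description, sample size and Table 1) and in Sections 6.1, 10.2 and 12.9.

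- **If the 14 listed centres are current:** state a maximum of 4,750 patients and 700 images, and replace 17 with 14 in Section 6.1.
- **If 17 centres are intended:** add the three missing centres and their caps to Table 1, and change 14 to 17 in the synopsis. The added caps must total 650 if 5,400 is to stand. The ceiling of 850 images then stands.
- **In either case:** correct the Polish centre count in the Section 6.1 table to agree with its 300 x 3 allocation, and mark the 300 in the synopsis entry on planned numbers as per centre.

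The cost is protocol wording. Under the first option the stated study size becomes smaller, but no analysis changes.

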12.10 Procedures for Missing, Unused and Spurious Data

Missing values will not be substituted by estimated values, but treated as missing in the statistical evaluation. All data from all subjects dosed in the study will be included in all listings, plots, summary tables, and statistical analyses when appropriate.

12.11 Rules for Excluding Subjects from Analysis

All dosed subjects will be included in the analyses unless otherwise specified. The sponsor will make any decisions regarding whether any subjects or any individual values belonging to a subject will be excluded from the evaluations when the protocol violation is considered to have a negative impact on the scientific aspects and interpretation of the study results. Such judgments should be made in a blinded fashion before database lock and before any analyses have been performed. If the subject has received any GBCA, all available safety data will be used. The reason(s) for any exclusion will be described in the report.

12.12 Procedures for Reporting Deviations from Original Statistical Plan

Any deviations from the statistical analysis outlined in this protocol will be described, and reasons for the deviations listed, in the final Clinical Study Report.

13 SPECIAL REQUIREMENTS AND PROCEDURES

13.1 Regulatory, Institutional, and Ethical Review

Before starting this study, the protocol (authorised by the sponsor) will be submitted to the regulatory bodies/local health authorities (in accordance with local regulations) and to the Independent Ethics Committee (IEC) for evaluation. The protocol will also be signed by the principal investigator before submission to the IEC. The study will not start before the IEC gives written approval or a favourable opinion in accordance with ICH E6-GCP and all applicable regulatory bodies/local health authorities give approval or a favourable opinion as required.

No changes from the final approved (authorised) protocol will be initiated without the IEC's prior written approval or favourable opinion of a written amendment, except when necessary to eliminate immediate hazards to the subjects or when the change involves only logistics or administration. The sponsor will authorise and the principal investigator(s) will sign the protocol amendment prior to submission to the IEC. Protocol amendments should be submitted to the IEC without delay.

13.2 Ethical Considerations

Where IEC/Competent Authorities (CA) approval is required, the study can only begin after acquisition of a written approval/favourable opinion from the Committee/Authority. Where applicable, the approval/favourable opinion will contain:

- Identity of the study
- Date of review
- Documents reviewed
- List of names, titles and professions of the committee in the case of IEC favourable opinion

The original or copy of the approval/favourable opinion should be submitted to the Sponsor or Sponsor's designee.

The Investigator should submit accurate and adequate reports to the IEC/CA within the timelines as per local and national requirements.

13.3 Investigator's Responsibilities

13.3.1 Overall Responsibilities

The investigator(s) is/are responsible for conducting the study in full accordance with the Protocol and the Declaration of Helsinki, the *Good Clinical Practice: Consolidated Guideline*, approved by the ICH, and any applicable national and local laws and regulations. Information regarding any investigational centres participating in this study that cannot comply with these standards will be documented.

13.3.2 Subject Informed Consent

Written and oral information about the study in a language understandable by the subject will be given to all subjects. Each subject's willingness to participate in the study will be documented in a signed and dated informed consent form before any procedures or assessments are done and after the aims, methods, anticipated benefits, potential hazards, and insurance arrangements in force are explained. It will also be explained to the subjects that they are free to refuse entry into the study and free to withdraw from the study at any time without prejudice to future treatment. The informed consent process will be documented in the subject's medical record and the investigator will sign, date and time the informed consent form after the subject has signed, dated and recorded the time. The investigator(s) will keep the original consent forms and copies will be given to the subjects.

13.3.3 Direct Access to Source Data/Documents

The monitor(s), auditor(s), authorised personnel of the Sponsor/CRO, health authority inspector(s) or their agents, and authorised members of IECs will be given direct access to source data and documentation (e.g., medical charts/records, laboratory results, printouts, videotapes, etc.) for source data verification, provided that subject confidentiality is maintained in accordance with local requirements.

13.3.4 Confidentiality Regarding Study Subjects

The investigator(s) must assure that the privacy of the subjects, including their personal identity and all other personal medical information, will be maintained at all times. In eCRFs and other documents or image material (including materials from all examinations, e.g., CT, MR, CT, fluoroscopy, X-ray, SPECT, PET) submitted to the sponsor/CRO, subjects will not be identified by their names, but by an identification code (e.g., study subject number).

Personal medical information may be scrutinised for the purpose of verifying data recorded in the eCRF. This may be done by the monitor(s), properly authorised persons on behalf of the sponsor, the quality assurance unit, or regulatory authorities. Personal medical information will always be treated as confidential.

13.4 Protocol Deviations

Any deviation from the protocol when no approved amendment exists must be documented as a protocol deviation and reported according to local requirements. If appropriate, corrective and preventative action must be implemented to avoid repetition. Protocol deviations and any potential impact on the study results will be discussed during the reporting of the study.

Waivers or protocol exceptions will not be granted prospectively by the Sponsor under any circumstances.

